We are targeting recruitment of pregnant women who have a pre-pregnancy BMI 18.5 – 45.0 kg/m². We are specifically targeting women at high risk of excessive GWG during pregnancy. Data show 56% of women gain excessively^{3,4}. Excessive gestational weight gain (GWG) is associated with poor outcomes. Based on our data, we anticipate the following distribution among the 3 pre-pregnancy weight categories selected (BMI <24.9 = 40%; BMI 25-25.9 = 34%; BMI >30 = 26%). Due to the adverse health that is related to excessive GWG, it is imperative to seek interventions to prevent excessive GWG.

Data Safety and Monitoring Plan

Data security: All participants will be assigned a non-identifiable subject number. Data collected will be kept in [name] locked research laboratory. Only study personnel and [name] have keys to access this area. Electronic data will be kept on a password protected computer in [name] laboratory on the shared drive. Only personnel approved by HSC and on the protocol will have access to the data.

Data and safety monitoring plan: Monitoring will be handled by the PI and the research team.

INCLUSION OF WOMEN, MINORITIES, AND CHILDREN

Inclusion of Women: We are targeting pregnant women who have a pre-pregnancy BMI 18.5 – 45.0 kg/m². We are specifically targeting women at high risk of excessive GWG during pregnancy and at high risk of retaining a significant amount of body weight postpartum. Data show 56% of women gain excessively^{3,4} and that excessive gestational weight gain (GWG) is associated with poor outcomes.

Inclusion of Minorities: We are including all racial/ethnic groups in this study. There will be no exclusion criteria based on race or ethnicity.

Inclusion of Children: The study will include offspring born to women participating in the study.

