C1) Preliminary study: multiple goal behavioral lifestyle intervention to reduce excessive GWG: Drs. [name] and [name] were co-PIs funded on a pilot study to test the effectiveness of a multiple goal behavioral lifestyle intervention (vs. UC) to prevent excessive GWG using GBPC. The primary outcome was the proportion of women gaining excessively based on 2009 IOM recommendations⁶⁹. The intervention ran from 18 to 36 weeks and the intervention group met weekly by phone with a Dietitian for 60 minutes. All participants reported body weight weekly via text message. The curriculum included 18 lessons. Data are presented in Table 1. Fourteen women were enrolled into the multiple goal group and 12 women were enrolled into the UC group. We lost 3 subjects in the control group and lost zero subjects in the intervention. In the intervention group, 29% gained excessively while 78% of the UC group gained excessively. Additionally, the UC group gained more weight ($p=0.010$). Structured interviews were done in a sample of those completing the study ($n=9$). When asked, “What changes did you make due to the intervention?”, 33% responded, “consumed more fruits/vegetables” and “controlled portions” while 22% said “consumed less sugar”. When asked “What they liked about the program?”, 44% replied “monitoring body weight”. When asked “What they would recommend for future interventions?”, responses included, *keep a variety of topics and set one goal for the entire program*. The data are promising.

Table 1: Preliminary results from pilot study to prevent excessive GWG

	Pre-pregnancy BMI (kg/m ²)	GWG (kg)	% gaining excessively
Usual Care (n=9)	29.3 ± 4.8	18.4 ± 7.3	78%
Intervention (n=14)	28.4 ± 8.6	11.8 ± 4.0*	29%

Means ± SD

*Significantly different from control group ($p=0.010$)

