C5c) Hfib intervention details: The 60-minute weekly group sessions (18 total) will focus on eating a high fiber diet both during and after pregnancy. The dietary reference intake (DRI) for fiber during pregnancy is 28 g/day and 25 g/day for females of reproductive age⁵⁴. *The goal is for participants to gain within 2009 IOM recommendations⁶⁹.* To achieve this, all participants will be encouraged to consume ≥ 30 g/day of fiber. The Hfib intervention will receive a fiber goal (no calorie goal). This is intentional because we want to remove the driver of what is known to induce weight loss (calorie goal) and determine if a fiber goal without a calorie goal can *blunt* excess GWG. Because the goal is to keep the Hfib intervention simple, we are focusing on the one behavior with the best evidence to control weight gain; consuming ≥ 30 g/day fiber. Discussion will encourage problem solving, provide educational information, and social engagement during the video calls. Participants will be taught to track their daily total fiber intake in REDCap. Participants will be encouraged to follow a balanced diet emphasizing fruits and vegetables, whole grains, low-fat dairy and lean protein. General PA recommendations during pregnancy will be mentioned but no focus or reinforcement of this behavior will take place. All participants will be given a body weight scale and report body weight weekly. Participants will receive a notebook containing handouts and assignments specific to each weekly topic. Dietitians will facilitate the lessons and lead discussion.

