Maternal olfactory testing	•	•		•		•
Maternal urine	•	•	•	•	•	•

Maternal cognitive testing	•	•		•	•	•
Maternal stool	•	•		•	•	•
Maternal blood draw	•	•		•	•	•
Maternal actigraphy	•	•		•	•	•
Infant anthropometrics			•	•	•	•
Infant skin folds			•	•	•	•
Infant body composition (PeaPod)			•	•	•	•
Infant stool			•	•	•	•
Infant DXA scan			•			•
Infant diet recalls			•	•	•	•
Breast milk				•	•	
Satisfaction survey (Hfib only)		•				
Process evaluation (Hfib only)		•				

C7a) Gestational weight gain: GWG will be calculated following the NIH LIFE-Moms protocol¹⁰⁶. Self-reported pre-pregnancy weight will be replaced with baseline study measured body weight and subtracted from weight measured at 34 weeks to calculate GWG. When data are missing, we will extract body weight at delivery admission from the electronic medical record. GWG guidelines will be used to classify excessive GWG⁶⁹.

C7b) Questionnaires: Questionnaires will be given to assess maternal pregnancy and infant birth characteristics at study visits, via REDCap surveys, and over the phone throughout the study. Examples include maternal health (medical and obstetric history), self-reported race/ethnic background, income, education, household information (marital status, baby father's health, etc.), hunger and satiety, emotional health, gastrointestinal health, supplement use, alcohol consumption, drug use, infant sex, birth weight, birth length, and gestational age, to name a few¹⁰⁷⁻¹⁰⁹. One survey will ask about liking or disliking of foods to assess perception of taste and olfaction, which can influence what foods people choose to eat. The survey will be taken through a link (https://uconn.co1.qualtrics.com/jfe/form/SV_aVFeLIsOTSVSCzk) which is hosted by the University of Connecticut and the corresponding data will be stored on their server. Once the survey has been scored, the results will be sent to the study team. No identifying information except a participant ID will be included in the survey.

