C7i) Process evaluation: Data will be collected throughout the intervention to assess barriers to recruitment and study retention, participant acceptability and intervention adherence, and how well the intervention was implemented. Participants that drop will be contacted and asked to complete a brief interview to provide feedback. Semi-structured interviews will be conducted at the final assessment (34 wks). Participants will be asked about their perception of the intervention including both positive and negative aspects and any challenges that were encountered, pros and cons of using group video counseling to promote healthy behaviors during pregnancy, and their overall satisfaction with the intervention. Interviews will be audio recorded and transcribed verbatim. Comments will be coded, categorized into themes and used to refine and further develop future interventions.

C7j) Safety monitoring: All subjects will be given a body weight scale and report body weight weekly. This allows close supervision of progression of each participant to ensure the intervention is not overly effective and all women are gaining adequate body weight. If a woman gains or loses more than 5 lbs over a two-week period, she will be flagged and contacted. If she is in the Hfib group, total weight gain recommendations will be reviewed and her dietary habits and fiber intake will be reviewed and reinforced. Rapid weight changes or any other safety concerns will be reviewed by our study physician for safety purposes. The participant's provider will be notified if physician deems necessary.

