(7) *Plan for monitoring and reporting problems.* Adverse events will be assessed every 4 weeks during the dietary recalls during the 18-week intervention in the high-fiber group only. Baseline measurements will not be assessed for adverse events. Only adverse events related to gaining or losing too much weight or allergic reactions to the study food will be recorded. Research staff will immediately report any adverse events to the study PI for review. The study physician will review maternal and infant abnormal findings. If recommended by the study physician, abnormal findings will be communicated to the participant's physicians or infant's pediatrician.

(8) *Plan for handling study withdrawal/discontinuation.* Participants may discontinue study participation at any time in the study. Participants will be asked to sign a withdrawal consent. If participant does not sign a withdrawal consent, only data collected prior to withdrawal will be used.

Adequacy of Protection Against Risks

Describe plans for the recruitment of subjects and the consent procedures to be followed. Recruitment will be open to all pregnant women that meet the study inclusion criteria. The KUMC IRB will review and approve this study prior to implementation. Recruitment will only be performed under the supervision of the PI by trained research personnel who have completed human subjects and HIPAA training. Personnel will identify subjects who might be eligible by screening their electronic medical record in O2. Only medical information related to inclusion/exclusion criteria will be looked at. If determined eligible, research personnel will visit the patient at their scheduled clinic visit. OBGYN clinic staff will introduce study to potential subjects. Research personnel will discuss the study in detail and determine final eligibility. Participants missed at their OBGYN visit will be contacted via phone. If participants are interested, they will be followed up with via phone or email to determine enrollment and complete the informed consent. Informed consent will be obtained via phone or in person at the first study visit.

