Protection against risk. Although no appreciable risk of physical or mental harm is expected to result from the protocol, procedures for dealing with adverse effects are established. Subjects will be instructed to report immediately to the study coordinator if any health problem occurs and to call the PI ([name]) at any time if they have questions or concerns. In such an event, it is the PI responsibility to answer those concerns honestly and to reiterate to the subject that they should continue in the trial only if they feel entirely comfortable with it. Subjects who choose to withdraw from the study will be reassured if they indicate the desire to withdraw.

Subjects will be protected against the risk of breaking confidentiality by decoupling of names from databases. Each participant will be assigned a numerical study ID and informed consent forms that include the subject's signature will be stored separately in locked file cabinets. For ensuring confidentiality, these are generally acknowledged to be the best methods known for ensuring that names are not associated with data. Only selected research staff will have access to the subjects' data. Subjects' informed consent includes the HIPAA compliance documentation approved by the KUMC IRB. Research team personnel will abide by all tenets of the University confidentiality policies as well as the Privacy Protection for Research Subjects.

Potential Benefits of Proposed Research

Describe all potential benefits. There are no direct benefits for participation in the study outside of contributing to the knowledge and formulation towards interventions that are successful at helping women to achieve appropriate GWG. This study could contribute to ways to improve maternal and infant health outcomes of pregnant women by improving GWG by identifying novel methods that can be used to encourage appropriate GWG.

Importance of Knowledge to be Gained

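### The scheduled adverse-event enquiry covers only the high-fiber arm and two event types, so its record cannot be compared by arm; gain below the guideline range is not classified

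*Combined protocol and SAP*

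**What the plan says.** **Adverse events.** Risks to Human Subjects, item (7), sets the schedule: "Adverse events will be assessed every 4 weeks during the dietary recalls during the 18-week intervention in the high-fiber group only". Baseline is left out. The same item limits content: "Only adverse events related to gaining or losing too much weight or allergic reactions to the study food will be recorded". No section describes a matching enquiry in usual care. The section on protection against risk does address every participant: "Subjects will be instructed to report immediately to the study coordinator if any health problem occurs". It does not say whether such reports enter the adverse-event record.

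**Other safety data, not limited by arm.**
- Weekly weights: C5c, C5e, C7j.
- A rapid-change flag, in C7j: "If a woman gains or loses more than 5 lbs over a two-week period, she will be flagged and contacted".
- Physician review of rapid weight change and other safety concerns: C7j.
- Questionnaires that include gastrointestinal health: C7b, Table 4.
- Blood pressure: C7m.
- Extraction of maternal and infant health information from the medical record: item (3).
- A statement in C2 and item (2) that women who develop one of the listed exclusion conditions in pregnancy will be taken into account in the final analysis. No method is given.

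**Weight gain.** C5c states: "The goal is for participants to gain within 2009 IOM recommendations". C7j says that weekly weights serve to "ensure the intervention is not overly effective and all women are gaining adequate body weight". On classification, C7a says only: "GWG guidelines will be used to classify excessive GWG". C9 compares weight gain between groups by t-test. It contains no adverse-event analysis and no analysis of inadequate gain.

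**The concern.** An adverse-event count depends on how often, and about what, people are asked. Here one arm is asked on a schedule and the other is not. Any comparison built on that record would mix the effect of the diet with the effect of asking. The content limit adds to this: gastrointestinal tolerability, an obvious question for a fiber diet, has no place in the adverse-event record of either arm.

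The second gap is in the weight data. The trial aims for gain inside a range and states a worry that the intervention could work too well. A lower mean gain, or fewer women gaining excessively, does not show whether women moved into the range or below it.

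C9 describes the purpose as feasibility data, and C11 looks ahead to a next study. That study would need safety counts collected in the same way in both arms, and a three-way split of gain.

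**Working it through.** The documents give no event rate, power or precision figure for safety, so there is no stated figure to reproduce. The check compares the sections and adds simple arithmetic.

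**1. Scheduled enquiries per arm.** Inputs are a 4-week interval and an 18-week intervention, from item (7).
- Starting at week 4: weeks 4, 8, 12 and 16, which is 4 enquiries.
- Starting at week 2: weeks 2, 6, 10, 14 and 18, which is 5 enquiries.
- Usual care: 0.

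**2. What unequal recording could do.** Item (7) attaches the arm limit to the enquiry. It does not say whether a weight event noticed in usual care is also entered as an adverse event. Take 28 per arm (half of 56; equal allocation is an assumption) and the same true rate p of weight events in both arms (also assumed). The expected high-fiber count is 28p. The usual-care count runs from 0 (never entered) to 28p (always entered).
- p = 10%: 2.8 against 0 to 2.8, an apparent difference of 0 to 10 points.
- p = 20%: 5.6 against 0 to 5.6, an apparent difference of 0 to 20 points.

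The upper ends require that no usual-care event is entered. They are bounds under that reading and not estimates.

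**3. What an excessive-only classification leaves out.** C1 reports for the pilot: "In the intervention group, 29% gained excessively while 78% of the UC group gained excessively".
- Intervention: 29% of 14 is 4 women, leaving 14 − 4 = 10 (71%) not split into within and below range.
- Usual care: 78% of 9 is 7 women, leaving 9 − 7 = 2 (22%) not split.

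The pilot tested a different, multiple-goal intervention. It shows what the classification omits and says nothing about the rate of low gain in this trial.

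**4. Whether the flag fills that gap.** It needs a change of more than 5 lb within two weeks. A woman whose weight stays constant for all 18 weeks has a two-week change of 0 lb throughout and never meets it. Item (7) covers excess gain or loss and does not name too little gain.

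**5. Interval over which gain is measured.** C7a subtracts the baseline study weight from the weight at 34 weeks. Table 4 puts baseline at 12 to 20 weeks, so the interval is 34 − 20 = 14 to 34 − 12 = 22 weeks. When data are missing, delivery-admission weight is used, which lengthens it. Whole-pregnancy ranges applied to such an interval would count too many women as below range.

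**6. Precision of an even-handed comparison.** The 95% half-width of a risk difference is 1.96 × √(2p(1 − p)/28).
- p = 10%: 1.96 × √(0.18/28) = 15.7 points.
- p = 20%: 1.96 × √(0.32/28) = 21.0 points.

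**The case against.** The strongest reply is that the harm depends on an analysis nobody planned. Item (7) belongs to a human-subjects monitoring plan. C9 has no by-arm adverse-event comparison, and study-food allergy naturally concerns the arm given the snacks. Weights, flags, gastrointestinal questionnaires and record extraction exist in both arms and can be tabulated evenly whatever they are called. With about 28 women per arm, even a well-collected comparison would be imprecise: the half-widths in step 6 exceed the largest distortions in step 2 at the same rates.

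Most of this stands, and it limits the point. A reader might infer that usual-care women have no safety data or go unmonitored; the sections listed above contradict that. A reader might also infer that pregnancy complications have no place in the analysis; C2 and item (2) give the listed conditions one, though without a method. Nor do the documents support saying that a planned result is biased, or that a spurious difference of 10 or 20 points is to be expected. Those figures rest on assumed rates and a zero-capture reading.

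The reply does not remove the unequal enquiry, which follows directly from item (7). It also leaves low gain unclassified: the weights are collected, but no section says they will be used for that purpose.

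**Conclusion.** The point holds in a limited form. As written, item (7) produces an adverse-event record with 4 or 5 scheduled enquiries in one arm and none in the other, restricted to two kinds of event. That record can describe the high-fiber arm but cannot support a comparison by arm. No such comparison is planned, the efficacy analyses are unaffected, and other safety data cover both arms.

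Separately, the aim of gain within the guideline range and the stated concern for adequate gain are not matched by any classification of low gain, and the rapid-change flag cannot stand in for one.

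The enquiry counts and the classification gap follow from the text. The sizes in steps 2 and 6 rest on assumed rates of 10% and 20% and on 28 per arm.

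**What to change.** **Adverse events.** Keep the existing high-fiber enquiry, so that live questioning by staff is not lost in the intervention arm. Add to both arms one identical 4-weekly REDCap item, attached to the weekly weight report, covering weight concerns, gastrointestinal symptoms and new medical or obstetric problems. Base any by-arm table on this common item only. Report study-food allergy and recall-based events as descriptions of the high-fiber arm.

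**Descriptive tables by randomised arm, from data already planned.**
- The rapid-change flags.
- Gastrointestinal symptoms from the questionnaire.
- The conditions listed in C2 and item (2).
- Gain below, within and above range, with the range matched to each woman's actual measurement interval and not to whole-pregnancy totals. Women whose final weight comes from delivery admission should be shown separately.

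**Costs and limits.** The work is one short item, a few tabulations, and staff review of a broader event list in both arms. Usual-care women have slightly more contact. Identical wording does not remove every ascertainment difference, because high-fiber women also have 18 weekly sessions, daily logs and dietitian calls; this should be stated with the results. Precision stays low, at about ±16 to ±21 points under the assumptions above.

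**Separate matter.** The high-fiber enquiry is tied to dietary recalls that C5f schedules every two weeks (9 in total) and C7d every four weeks. Those sections must be reconciled.
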